10.2. Populations for Analyses

The following populations will be defined for this study:

Intention-to-Treat (ITT) population: will include all enrolled patients. This population will be used for all baseline, efficacy, and health economics analyses. All patients in the ITT population will be considered to have completed the study.

Per-protocol population: will include all enrolled patients who receive at least one dose of study treatment and do not have any major protocol violations that could potentially affect the efficacy conclusions of the study. This population will be defined in detail in the statistical analysis plan (SAP) prior to database lock.

Safety population: will include all enrolled patients who received any quantity of study treatment, regardless of their eligibility for the study. The safety evaluation will be performed based on the first dose of study treatment a patient actually received. The safety population will be used for all dosing/exposure, and safety analyses.

Pharmacokinetic population: will include all enrolled patients who received at least 1 full infusion of LY2606368 and have evaluable PK samples collected.

Biomarker population: will include the subset of patients from the ITT population from whom a valid assay result has been obtained.

10.3. Statistical Analyses

Statistical analysis of this study will be the responsibility of Lilly or its designee.

All tests of treatment effects will be conducted at a 1-sided alpha level of 0.1, unless otherwise stated. Unless otherwise stated, all confidence intervals (CIs) will be given at a 2-sided 95% level.

Any change to the data analysis methods described in the protocol will require an amendment only if it changes a principal feature of the protocol. Any other change to the data analysis methods described in the protocol, and the justification for making the change, will be described in the SAP and the clinical study report. Additional exploratory analyses of the data will be conducted as deemed appropriate.

10.3.1. Efficacy Analyses

Overall response rate (ORR) is defined as the number of patients who achieve a best overall response of CR or PR, divided by the total number of patients enrolled to the corresponding cohort (ITT population). Complete or partial responses may be claimed only if the criteria for each are met at a subsequent time point (greater than 4 weeks). The ORR, with 95% and 80% CIs, will be summarized for each cohort using the Clopper-Pearson method.

Disease control rate (DCR) is defined as the number of patients who achieve a best overall response of CR, PR, or stable disease (SD) divided by the total number of patients enrolled to the corresponding cohort (ITT population). The confirmation of CR and PR is required. In the case of SD, measurements must have met the SD criteria at least once after study entry at a minimum interval (in general not less than 6 weeks). The DCR, with 95% CI, will be summarized for each cohort using the Clopper-Pearson method.

Duration of response is defined as the time from the date measurement criteria for CR or PR (whichever is first recorded) are first met until the first date that disease is recurrent or objective progression is observed, per RECIST 1.1 criteria, or the date of death from any cause in the absence of objectively determined disease progression or recurrence.

Overall survival is defined as the time from enrollment until death from any cause. If the patient is alive or lost to follow-up at the time of data analysis, OS data will be censored on the last date the patient is known to be alive. Overall survival curves, the median and survival rates at various time points with 95% CI, for each cohort will be estimated using the Kaplan-Meier method (Kaplan and Meier 1958).

Progression-free survival is defined as the time from enrollment until the first radiographic documentation of progression or death from any cause in the absence of PD. Patients known to be alive and without disease progression will be censored at the time of the last adequate tumor assessment prior to study completion (a detailed PFS event/censoring scheme is provided in SAP). Progression-free survival curves, median PFS, and PFS rates at various time points with

95% CI for each cohort will be estimated using the Kaplan-Meier method (Kaplan and Meier 1958).

Exploratory sensitivity analyses on efficacy endpoints may be conducted as described in the SAP.

10.3.2. Safety Analyses

All patients who receive at least 1 dose of any study therapy will be evaluated for safety and toxicity.

The Medical Dictionary for Regulatory Activities (MedDRA™) Version 18.0 (or higher) will be used when reporting AEs by MedDRA terms. The MedDRA Lower Level Term will be used in the treatment-emergent computation. Treatment-emergent adverse events will be summarized by System Organ Class (SOC) and by decreasing frequency of Preferred Term within SOC.

Safety analyses will include summaries of the following:

- AEs, including severity and possible relationship to study drug
- SAEs, including possible relationship to study drug
- AEs leading to dose adjustments
- discontinuations from study treatment due to AEs or death
- treatment-emergent abnormal changes in laboratory values
- treatment-emergent abnormal changes in vital signs and ECGs

10.3.3. Other Analyses

10.3.3.1. Patient Disposition

A detailed description of patient disposition will be provided, including a summary of the number and percentage of patients entered into the study and enrolled in the study, as well as number and percentage of patients completing the study, as defined in the SAP, or discontinuing (overall and by reason for discontinuation). A summary of all important protocol deviations will be provided.

10.3.3.2. Patient Characteristics

Demographic data are collected and reported to demonstrate that the study population represents the target patient population considered for regulatory approval.

A summary of baseline patient and disease characteristics, historical diagnoses, preexisting conditions, and prior therapies will be reported using descriptive statistics.

10.3.3.3. Concomitant Therapy

A summary of prior and concomitant medications by treatment cohort will be reported.

10.3.3.4. Poststudy-Treatment-Discontinuation Therapy

The numbers and percentages of patients receiving post study-treatment-discontinuation anticancer therapies will be provided by type of therapy (surgery, radiotherapy, or systemic therapy), and by drug class and/or name, overall and by line of therapy.

10.3.3.5. Treatment Compliance

The number of cycles received, dose omissions, dose reductions, dose delays, and dose intensity will be summarized for all treated patients by treatment cohort.

Study treatment will be administered at the investigator site, therefore treatment compliance is assured.

10.3.3.6. Pharmacokinetic/Pharmacodynamic Analyses

Pharmacokinetic parameter estimates for LY2606368 will be estimated by standard population PK methods of analysis using validated PK software programs (for example, NONMEM) and that is approved for use by Global PK/pharmacodynamic management. The version of any software used for the analysis will be documented, and the program will meet the Lilly requirements of software validation.

Sparse LY2606368 PK data obtained from patients who receive at least 1 dose of LY2606368 and have had samples collected for PK analysis will be pooled with PK data from a previous study investigating LY2606368 as monotherapy (Study JTJA) and analyzed by population-based PK analysis methods to characterize the observed intra- and interpatient PK variability and identify the patient-specific covariates that contribute to the observed PK variability of LY2606368. Post-hoc LY2606368 PK parameters estimates will be calculated for each patient in this study and will include the maximum plasma concentration (C_{max}), area under the plasma concentration versus time curve (for example, $AUC_{[0-72]}$, $AUC_{[0-\infty]}$), terminal elimination half-life ($t_{1/2}$), systemic clearance, and the multi-compartmental volumes of distributions (for example, V_1 , V_2 , and V_{ss}). A descriptive summary of LY2606368 plasma concentration data will also be provided for the LY2606368 C_{max} , minimum plasma concentration (C_{min}), and accumulation ratio across multiple cycles of treatment.

Additional exploratory analyses, such as population-based analyses that examine the relationship between LY2606368 exposure (PK) and response and/or safety, may be performed (if the data warrant).

Interim review of the clinical PK data after the first 29 patients enrolled in both Cohorts 1 and 2 may be conducted.

10.3.3.7. Biomarker Analyses

Descriptive summaries and statistical analyses results will be provided to support the biomarker research objectives outlined in Section 9.8.

Appropriate descriptive statistics for biomarker results based on pre-treatment, on-treatment, or post-progression samples will be reported. Each biomarker will be described using summary statistics at the study, treatment arm, and at the level of other patient subgrouping of interest. Any correlations or associations between the biomarkers measured on the same patient will also be looked at.

In particular, descriptive summaries of biomarkers obtained from biopsies done on lesions that regressed after treatment will be provided. Provided a sufficient number of patients with such

biopsies are available, additional analyses may be undertaken to investigate the correlation between the change in the status/level of the biomarker and the change in the size of the lesion.

All biomarkers deemed relevant may be specifically investigated with the aim of understanding the genetic profile of patients who receive the greatest clinical benefit from LY2606368. These investigations will look at the correlation/association between the baseline (archival or pre-treatment) status/level of the biomarker(s) and measures of clinical benefit such as objective clinical response status (CR/PR or no-CR/PR) or disease control status (CR/PR/SD or no-CR/PR/SD). Where a change in the status/level of a biomarker over time can be ascertained, additional exploratory analyses may be undertaken to assess the effect of the change or its magnitude on the same clinical efficacy endpoints. For secondary efficacy measures of PFS and OS, parametric and semi-parametric survival analysis will be undertaken to quantify the association between the biomarker status and the time-to-event efficacy measure.

For serially measured plasma-based biomarkers, change from baseline to subsequent time points may be associated with clinical response outcomes. In addition, the time-course relationship of these biomarkers with safety and/or PK outcomes may also be investigated.

Biomarker results may also be analyzed to elucidate the associations between the baseline status/level, or change in status/level and including, but not limited to, the mechanism of action of LY2606368, sensitivity to CHK1 inhibition, and sensitivity or resistance to platinum-based therapies.

10.3.3.8. Health Outcome/Quality of Life Analyses

For the LCSS, the compliance rate by cohort will be calculated as the number of completed assessments divided by the number of expected assessments (that is, patients still on study). Compliance rates, reasons for noncompliance, and data collected will be summarized by cohort. Descriptive statistics for each of the domain scores/items of interest by category of best overall response (that is, CR, PR, SD, PD) will be summarized and a linear model will be fitted for each cohort in order to evaluate the association between best overall response and change from baseline/the maximum improvement from baseline in lung cancer-specific symptoms, symptomatic distress, activity status, overall quality of life, total LCSS score, and ASBI for patients who have platinum-sensitive or platinum-resistant/refractory SCLC. The model will include change from baseline/maximum change from baseline as the response variable and category of best overall response as an independent variable. The ASBI will be calculated as the mean of 6 symptom-specific questions; the total LCSS score will be calculated as the mean of 9 questions from the LCSS. For a given assessment, if any of the 6 symptom-specific questions have not been completed, the ASBI will not be calculated. Similarly, if any of the 9 LCSS questions have not been completed, the total LCSS score will not be calculated.

10.3.4. Interim Analyses

For each cohort, one interim analysis of futility will be conducted after the 29th patient in the cohort has completed Cycle 3, and, if required, the response is confirmed. The interim analysis will be conducted to assess whether the respective cohort is unlikely to achieve statistical

significance on its primary endpoint and may also include PK data in order to confirm that patients are in the expected exposure range.

The stopping rule for interim analysis is defined as follows:

- Platinum-sensitive cohort:
 - If 4 or fewer confirmed overall responses (CR or PR) are observed in the first 29 patients, then the cohort will be terminated; otherwise, the cohort will continue.
- Platinum-refractory/resistant cohort:
 - If 0 confirmed overall responses (CR or PR) are observed in the first 29 patients, then the cohort will be terminated; otherwise, the cohort will continue.

11. References

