	Plasma biomarker sample	X				X		Collect prior to dosing on Day 1 of Cycles 1 and 3 only.
	ECG	X		X		X		Single local ECG collected at each time point. Day 1: predose, 10 min after EOI (±5 min), 30 min after EOI (±10 min), and >1 hour after EOI. Cycle 2-X: predose. However, if QTcF >480 msec is observed on Day 1, then 10 min after EOI (±5 min), 30 min after EOI (±10 min), and >1 hour after EOI should also be collected in subsequent cycles.
Optional Tumor Biopsy			X				Can occur at any time during patient's treatment.	

Study Period		Study Treatment Period						
		1		2		3-n ^a		
Cycle/Visit		14 days		14 days		14 days		
Duration		14 days		14 days		14 days		
Relative Day within Dosing Cycle		1	8	1	8	1	8	
Tumor Assessment	Radiologic imaging according to RECIST 1.1						X	For the first 52 weeks following enrollment, perform approximately every 6 weeks starting at the end of Cycle 3 (eg, Days 8-14). Thereafter, perform approximately every 12 weeks. The scanning interval (6 or 12 weeks [± 1 week]) should be maintained even if cycles are delayed. As a result, after Cycle 3, the scans may not always occur at the end of a cycle. The same method of imaging used at baseline should be used for each subsequent assessment. Scans should also be obtained as clinically indicated.
Tumor Assessment	Tumor measurement (palpable or visible)						X	Perform at least every 6 weeks starting in Cycle 3 on the same day as the radiologic imaging.
Adverse Events Collection/ CTCAE Grading		X		X		X		
Concomitant Medication Notation		X		X		X		
Lung Cancer Symptom Scale		X		X		X		The LCSS is to be administered prior to extensive interaction with site personnel and prior to administration of study drug.
Study Treatment	LY2606368	X		X		X		IV over approximately 60 (+10) min

Abbreviations: BSA = body surface area; CT = computed tomography; CTCAE = Common Terminology Criteria for Adverse Events (NCI 2009); ECG = electrocardiogram; ECOG = Eastern Cooperative Oncology Group (Oken et al. 1982); EOI = end of infusion; IV = intravenous; min = minute; LCSS = Lung Cancer Symptom Scale; PK = pharmacokinetic; QTcF = QT interval using Fridericia’s correction; RECIST 1.1 = Response Criteria In Solid Tumors Version 1.1 (Eisenhauer et al. 2009).

Table JTJH.2.3. Post-Treatment Follow-Up Schedule of Activities

Study Period		Post-discontinuation Follow-Up		
		Short-term Follow-Up	Long-term Follow-Up	
Duration		30 ± 5 days	60 ± 14 days	
Visit		801	802-X	

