10.1. Sample Size Determination

The study will enroll approximately 116 patients (58 platinum-sensitive patients, 58 platinum-refractory/resistant patients).

For the platinum-sensitive cohort, it is assumed that a true overall response rate (ORR) of less than 20% indicates inadequate antitumor activity. Given that a futility interim analysis will be conducted on the first 29 patients' response data, then with a one-sided significance level of 0.1, a sample size of 58 patients will provide approximately 90% power to detect a true ORR of at least 35%, i.e. 16 or more confirmed overall responses (complete response [CR] or partial response [PR]) are observed in all 58 patients.

For the platinum-refractory/resistant cohort, it is assumed that a true ORR of less than 5% indicates inadequate anti-tumor activity. Given that a futility interim analysis will be conducted on the first 29 patients' response data, then with a one-sided significance level of 0.1, a sample size of 58 patients will provide approximately 90% power to detect a true ORR of at least 15%, i.e. 6 or more confirmed overall responses (CR or PR) are observed in all 58 patients.

For each cohort, the overall type II error rate, i.e. the probability of terminating an effective cohort, will be controlled using a Lan-DeMets spending function (Lan and DeMets 1983), which generates boundaries that are very similar, though not identical, to the classical stopping boundaries of O'Brien and Fleming (1979). The type II error rate spent at interim analysis after the first 29 patients for each cohort is approximately 2%; the cumulative type II error rates spent at final analysis for platinum-sensitive cohort and platinum-refractory/resistant cohort are 9.9% and 9.4%, respectively.

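### The futility look sets no minimum follow-up beyond the 29th patient's Cycle 3, so patients stable after one scan count towards a mandatory stop although a later response would count in the final ORR

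*Protocol*

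**What the plan says.** Protocol 10.3.4 times the single futility look in each cohort: it is "conducted after the 29th patient in the cohort has completed Cycle 3, and, if required, the response is confirmed". SAP 5.16 repeats this. The rule for the platinum-sensitive cohort (Cohort 1) is "If 4 or fewer confirmed overall responses (CR or PR) are observed in the first 29 patients, then the cohort will be terminated". For the platinum-refractory/resistant cohort (Cohort 2) the limit is 0 confirmed responses among the first 29. SAP 5.1 repeats both rules.

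Three other places fix what is known at that moment:

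- **Scans.** A cycle is 14 days (Protocol 7.2.1). Table JTJH.2.2 has sites "perform approximately every 6 weeks starting at the end of Cycle 3", so the first post-baseline scan falls at about week 6 and the second at about week 12.
- **Confirmation.** A CR or PR counts only if its criteria are met again more than 4 weeks later (Protocol 10.3.1, SAP 5.10.1).
- **Final endpoint.** SAP 5.10.1 takes best response over the whole time on study treatment.

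Neither document sets a minimum follow-up beyond Cycle 3, says how patients who are stable and still on treatment are handled at the look, or pauses enrolment for it.

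**The concern.** The interim and final analyses give the same patient different windows in which to respond. A patient who is stable at week 6, still on treatment, and first meets PR criteria at week 12 is a responder in the final ORR once confirmed. If the look falls between those scans, that patient is one of the 29 but adds nothing to the response count. The confirmation clause does not help, because there is not yet a response to confirm.

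The error runs one way. Open outcomes can only lower the interim count, and a count at or below the limit ends the cohort. Protocol 10.1 and SAP 5.1 put the type II error spent at the interim at approximately 2%, with no allowance for outcomes still open. At stake is the chance of closing an active cohort.

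**Working it through.** **Inputs from the documents.** 29 patients at the look and 58 in all. Cohort 1: stop at 4 or fewer, succeed at 16 or more, null ORR 20% ("true overall response rate (ORR) of less than 20% indicates inadequate antitumor activity"), target 35% ("a true ORR of at least 35%, i.e. 16 or more confirmed overall responses"). Cohort 2: stop at 0, succeed at 6 or more, null 5% ("a true ORR of less than 5% indicates inadequate anti-tumor activity"), target 15%. Protocol 10.1 claims for each cohort that "with a one-sided significance level of 0.1, a sample size of 58 patients will provide approximately 90% power".

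**Assumed inputs.** *m* is the number of the 29 with only one scan at the look. *L* is the share of eventual confirmed responders whose response first appears after the first scan. The documents give neither, so both are varied.

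**Step 1: the plan's own figures, complete data.** With limit *s* and success threshold *r*, the false-stop probability is P(X₁ ≤ s), X₁ ~ Bin(29, p). Power is Σ over x > s of P(X₁ = x) · P(X₂ ≥ r − x), X₂ ~ Bin(29, p).

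- Cohort 1, p = 0.35: P(X₁ ≤ 4) = 0.0101, or 1.0%. Power 90.6%, which reproduces the stated figure.
- Cohort 2, p = 0.15: 0.85²⁹ = 0.0090, or 0.9%. Power 88.3%, within 2 points of the stated figure.

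The stated 2% is the nominal O'Brien-Fleming-type spend of β = 0.10 at half information: 2 − 2Φ(1.645/√0.5) = 0.020. The whole-number limits spend about half of it. Exact cumulative type II error is 9.4% for Cohort 1 (stated 9.9%) and 11.7% for Cohort 2 (stated 9.4%). The Cohort 2 gap does not come from the timing of the look and is not pursued here.

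**Step 2: some patients with one scan only.** The false-stop probability becomes P(A + B ≤ s), with A ~ Bin(29 − m, p) and B ~ Bin(m, p(1 − L)). If the cohort continues, hidden responders are credited at the final analysis: each single-scan patient without a visible response is a late responder with probability pL/(1 − p(1 − L)).

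Examples:

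- Cohort 1, m = 29, L = 0.2: p(1 − L) = 0.28 and P(Bin(29, 0.28) ≤ 4) = 0.061.
- Cohort 2, m = 15, L = 0.3: 0.85¹⁴ × 0.895¹⁵ = 0.1028 × 0.1894 = 0.0195.

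Results at the target ORR, for L = 10 / 20 / 30%:

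| Cohort | m | False stop (%) | Power (%) |
|---|---|---|---|
| 1 | 0 | 1.0 | 90.6 |
| 1 | 6 | 1.2 / 1.5 / 1.8 | 90.5 / 90.4 / 90.2 |
| 1 | 10 | 1.4 / 1.9 / 2.6 | 90.4 / 90.2 / 89.8 |
| 1 | 15 | 1.7 / 2.7 / 4.1 | 90.3 / 89.7 / 88.8 |
| 1 | 29 (bound) | 2.6 / 6.1 / 12.7 | 89.8 / 87.4 / 82.1 |
| 2 | 0 | 0.9 | 88.3 |
| 2 | 15 | 1.2 / 1.5 / 1.9 | 88.1 / 88.0 / 87.7 |
| 2 | 29 (bound) | 1.5 / 2.5 / 4.0 | 88.0 / 87.4 / 86.4 |

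**Step 3: what the bound requires.** The 29th patient is at week 6 at the look. With scans every 6 weeks (± 1 week), anyone enrolled more than about 6 to 7 weeks earlier has reached a second scan. So m = 29 needs all 29 to enrol within about 6 to 7 weeks.

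**Simplifications.** Patients with two scans are treated as fully observed, which understates the effect. Any second scan that a confirmation wait gives to stable patients is ignored, which overstates it.

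**The case against.** The strongest reply is that the plan has room for this. It declares about 2% at the interim and spends about 1%. With 10 single-scan patients and a 20% late share, Cohort 1 is still at 1.9%. Cohort 2 stays just under 2% even with 15 patients and 30%. Unless about half of the 29 are immature, Cohort 1 power stays close to 90%. All of this stands, and it limits the point to an improvement.

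The confirmation clause may also help more than the table shows. If it covers a pending response in any of the 29, the wait of more than 4 weeks will often run to the next scan, and stable patients get a second scan too. But the text does not say whether it means the 29th patient's response or anyone's, and it gives no wait when no response is pending.

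A reader might infer stronger things that the documents do not support:

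- *That power drops to 82% and false stopping reaches 12.7%.* This needs all 29 on one scan and a 30% late share. Nothing in the documents supports either. At that accrual speed, with no pause in enrolment, patients 30 to 58 would be nearly all enrolled by the look, and stopping would save little.
- *That the look happens at the 29th patient's first scan whatever is pending.* It does not; a response already seen is given time for confirmation.
- *That the plan expressly scores stable patients as non-responders.* No sentence says so. It follows from counting only confirmed responses among the 29.
- *That the false-positive rate rises.* It falls: in Cohort 1 at ORR 20%, from 10.2% with complete data to 8.1% if 30% of responses among the 29 are hidden.

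**Conclusion.** The point holds as a gap in the interim rule: follow-up at the look can be shorter than the endpoint needs, and the shortfall can only push towards termination. Its size cannot be fixed from the documents, because it rests on assumed accrual and time to response. For 10 to 15 single-scan patients and late shares of 10 to 30%, the Cohort 1 false-stop risk is 1.4% to 4.1%, against 1.0% with complete data and the declared 2% or so; power is 88.8% to 90.4%. Cohort 2 is at most 2.0% with up to 15 such patients and 4.0% at the bound. The effect is modest unless enrolment is fast, and Cohort 1 is the more exposed. The change is worth making because a wrong stop loses the cohort and the remedy is cheap.

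**What to change.** Add to Protocol 10.3.4 and SAP 5.16, with a cross-reference from SAP 5.1:

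*A cohort is terminated for futility only when the number of confirmed responses among the first 29 patients is at or below the limit (4 in Cohort 1, 0 in Cohort 2) and the unresolved patients among those 29 are too few to lift it above the limit. A patient is unresolved if still on treatment without PD and without a second scheduled post-baseline scan, or if a first response awaits confirmation. This applies to any of the 29. The second scan is a pragmatic cut-off, since best response runs to the end of treatment.*

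In Cohort 1, for example, 3 confirmed responses and 1 unresolved patient (at most 4) would stop at once; 3 and 2 (at most 5) would wait. If every late response first appears at the second scan, the false-stop risk returns to 1.0% and 0.9%. Responses first seen after the second scan can still be missed. The wording also settles whose response the confirmation clause means.

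**Cost.** Boundaries, sample size and treatment are unchanged. A decision to stop may come about 6 weeks later, or longer if a late response then needs confirming, and more patients may enter an inactive cohort meanwhile. In Cohort 2 a single unresolved patient is enough to delay a stop at 0 of 29. The plan already accepts a wait of this kind for confirmation.
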